#### **8.1.4.3 Reporting of Serious Adverse Events**

Adverse events classified as serious require expeditious handling and reporting to [REDACTED] to comply with regulatory requirements.

For any serious adverse event (SAE) that occurs from APR-246 consent up to 30 days after the last study drug administration, regardless of any opinion as to the relationship of the SAE to the study drug; or if any SAE that the Investigator feels is related to the study drug occurs later than 30 days after the last study drug administration, the [REDACTED]

[REDACTED]  
[REDACTED]  
[REDACTED]  
[REDACTED]  
[REDACTED]

All SAEs require that a Serious Adverse Event Report Form be completed and sent as a PDF via email (preferred method) or faxed to [REDACTED] at the address below within 24 hours of becoming aware of the event.

In the USA, SAEs will be reported to: [REDACTED]

[REDACTED]  
[REDACTED]  
[REDACTED]

#### **8.1.4.4 Safety Monitoring Committee**

The Safety Monitoring Committee, consisting of the Principal Investigator and Treating Investigator(s) (if different from the Principal Investigator), Sponsor and Medical Monitor, will perform a safety evaluation after the first 6 patients have completed 1 cycle of APR-246 and azacitidine combination therapy. Afterwards, safety will continue to be monitored and discussed during the regular study status meetings per the scheduled plan.

## **8.2 Efficacy Assessments**

Treatment response will be assessed by review of BM/BMA and flow cytometry at the protocol-specified timepoints. In the LTFU period, assessments may be performed per institutional standard frequency.

CBC and differential will also be used to assess the presence of blasts in PB, as well as the extent of hematopoietic recovery.

Disease assessment, according to the Investigator, will be determined at each assessment according to the modified International Working Group (IWG) response criteria appropriate to the patient's underlying disease (Cheson 2003, 2006).

### 8.3 ECGs

For all patients, ECGs will be read at the timepoints listed in Table 7. Patients with screening or any pre-dose QTc of  $450 \leq \text{QTc} < 470$  ms should be subject to more intense ECG monitoring described in Section 6.2.

**Table 7: ECG Timepoints**

Schedule	# of ECGs	Timing
Pre screening	TriPLICATE	N/A
Post-transplant, pre-screening (before APR-246)	TriPLICATE	N/A
Cycle 1, Day 1	Single or replicate	Pre-dose; EOI/Post dose (4 hrs. after SOI; +/- 30 min.)
Cycle 2, Day 1		Pre-dose; EOI/Post dose (4 hrs. after SOI; +/- 30 min.)
Cycle 3, Day 1		Pre-dose; EOI/Post dose (4 hrs. after SOI; +/- 30 min.)
Cycle 4, Day 1		Pre-dose; EOI/Post dose (4 hrs. after SOI; +/- 30 min.)
EOT		N/A

EOT: end of treatment; SOI=start of infusion; EOI=end of infusion

### 8.4 Pharmacokinetics

PK blood samples will be collected per Table 8.

**Table 8: PK Timepoints**

Cycle	Study Day	Nominal time	Time-point
Cycle 1	Day 1	0 hours	0-2 hrs prior to APR-246 infusion
		0.75 hours	45 minutes after start of infusion
		4 hours	+/-5 min relative to the end of infusion
		5-6 hours	60-120 min AFTER end of infusion
	Day 2	24 hours	0-2 hrs prior to APR-246 infusion on Day 2

## 8.5 Correlatives/Exploratory Studies

**Table 9: Biosampling Timepoints**

Cycle	Timepoint(s)	Window	Blood and Bone Marrow for chimerism	Blood for immune reconstitution	BMA for MRD	BM biopsy for IHC
pre-transplant	Baseline	-28 to -1 prior to HSCT			X	X
post-transplant, before APR-246/azacitidine	per institutional standard of care ♦	Day 1 to 100 post-transplant ♦	X	X		
APR-246/azacitidine treatment period	Baseline ¥	-28 to -1 prior to starting APR-246 and azacitidine			X	X
APR-246/azacitidine treatment period	end of C3, 6, 9, 12 (or EOT) ¥	up to 14 days	X		X	X
APR-246/azacitidine treatment period	end of C5 and 11	+/- 3 days		X		

♦ A patient could proceed to APR-246/azacitidine treatment as early as Day 30 post-transplant. Therefore sampling frequency will depend on institutional practices and patient status.

¥ Bone marrow aspirate sample and biopsy core are collected when bone marrow is sampled for disease assessment.

### 8.5.1 Donor/Recipient Chimerism

Post-transplant donor/recipient chimerism will be monitored every 3 months by PCR on CD3/CD33 cells according to local practice. Refer to Table 9.

### 8.5.2 Immune System Reconstitution

Post-transplant immune system reconstitution will be monitored every 6 months by flow cytometry on blood samples according to local practice. Refer to Table 9.

### **8.5.3 MRD by NGS**

Minimal/measurable residual disease (MRD) is monitored by a high-sensitivity NGS panel, including *TP53*, at a central laboratory. The *TP53* variant allele frequency (VAF) will be determined as a measure of MRD. Bone marrow aspirates will be obtained at pre-HSCT baseline, post-HSCT baseline, C3, C6, C9 and C12. Material for additional explorative biomarker research will be collected from the same samples. Refer to Table 9.

### **8.5.4 p53 IHC**

p53 protein expression as marker for cells with *TP53* mutation will be monitored by immunohistochemistry (IHC) at a central laboratory. Bone marrow biopsy cores will be obtained at pre-HSCT baseline, post-HSCT baseline, C3, C6, C9 and C12. Refer to Table 9.

### **8.5.5 Post-Transplant Engraftment**

Post-transplant donor engraftment via chimerism studies in blood and bone marrow will be summarized as continuous data for each dose level and overall respectively.

## 9.0 STATISTICS

Demographic and clinical variables for the study patients will be summarized using descriptive statistics (mean, standard deviation, median, inter-quartile range, range, frequency counts and percentages). Safety and efficacy data will be analyzed overall as well as separately for each dose cohort when appropriate.

### 9.1 Safety

Safety data including adverse events, vital signs, laboratory data, ECG, physical exam will be tabulated for the Safety Evaluable population which is all subjects who are registered on the study and received any dose of APR-246 or azacitidine. Adverse events will be tabulated by body system, preferred term, severity, and relationship to study drugs. The tabulation of laboratory parameters will include the normal ranges for each parameter. Each value will be classified as falling above, below, or within the normal range. Laboratory parameters will also be tabulated by maximum NCI-CTCAE v5 severity grade. Incidence and grade of acute and chronic GVHD at 1-year and cumulative will be summarized by number (%) of subjects for each dose level and overall.

### 9.2 Sample Size

The primary endpoint of the study is the relapse-free survival (RFS) at 12 months. The primary analysis will be done using the Kaplan-Meier method. Based upon the published data, the risk of relapse and non-relapse mortality in *TP53* mutated MDS is assumed to be ~40% and ~30% at 1 year, respectively. Thus the assumptions used for the sample size determination are:

- the null hypothesis: the RFS at 1 year is 30%,
- the alternative hypothesis: the RFS at 1 year is 50% or higher,
- accrual time: 24 months,
- follow-up time: 12 months,
- the RFS follows the exponential distribution.

With a one-sided significance level of 10%, 31 subjects will provide 90.1% power to test the null hypothesis against the alternative. The expected number of events during the study is 23 and the power was computed by a one-sided one-sample logrank test. The final analysis will be conducted when the follow-up time for all

censored patients exceed 12 months. The null hypothesis will be rejected if a one-sided p-value by the log-rank test is less than or equal to 0.1.

### **9.3 Efficacy Endpoint and Analyses**

All efficacy analyses will be provided by using Efficacy Evaluable population. All subjects who are registered on the study and received at least one dose of APR-246 or azacitidine, and have at least one efficacy assessment, or had relapse/progression.

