**Criteria for evaluation:**

Efficacy: Bone marrow aspirate and biopsy following cycle 3, cycle 6, cycle 9, and cycle 12, or when clinically indicated, and monthly CBC.

Safety: CTCAE v5.0. Weekly history and physical for AE assessment (CTCAE v5.0), including CBC with diff, CMP and LDH for the first month on treatment, then monthly.

GVHD assessment (Harris, 2016; Jagasia, 2015) will be performed weekly for the first month on treatment, then monthly.

PK: Cycle 1 only. Pre-dose, 45 min (+/- 5min) after SOI, at EOI (4 hr +/- 30 min after SOI), 5-6 hr after SOI, 24 hr after SOI/Day 2 (before Day 2 dose).

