**Efficacy Evaluable Population:**

All subjects who are registered on the study and received at least one dose of APR-246 or azacitidine, and have at least one efficacy assessment, or had

relapse/progression.

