### **Efficacy Analyses:**

All efficacy analyses will be provided by using Efficacy Evaluable population.

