#### 7.1.3 Post-Transplant, APR-246 Screening Period (Day 1 to 100)

Post-HSCT evaluation will occur as per institutional standard practices.

APR-246/azacitidine screening period occurs during Day 30 to 100 post-HSCT. The date will vary but should start (Day -28 relative to first dose) as soon as engraftment and the requirements in Section 7.1.4 are confirmed. The first dose must be administered no more than 28 days after confirmation.

The procedures listed below should be performed within 28 days prior to the first dose, or as indicated. Starred (\*) procedures should be done within 3 days prior to the first dose.

- Sign informed consent
- Disease assessment
- Eligibility
- Karnofsky performance status

- Medical history and Transplant Details
- Physical exam with Weight\*
- Vital signs\*
- CBC\*
- CMP\*
- ECGs\*; see Table 7.
- Pregnancy test (women of child-bearing potential only)\*
- Pre-treatment/baseline Bone marrow (BM)/Aspirate (BMA) for correlatives/exploratory: see Table 9
- GVHD monitoring
- Chimerism, immune reconstitution
- Monitor adverse events
- Concomitant medications

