#### **7.1.4 Confirmation to Proceed to APR-246 and Azacitidine Treatment (Day 30 to 100)**

- Bone marrow exam, including cytomorphology, cytogenetic assessment, and flow cytometry analysis.
- Engraftment is defined as  $ANC \geq 500/\mu L$  and platelets  $\geq 20000/\mu L$  on 3 consecutive measurements (each occurring at least 1 day apart). The patient must not have had a platelet transfusion within 7 days prior to the first measurement.
- Once this BM biopsy confirms CR and all other eligibility is confirmed, the patient must start APR-246 and azacitidine treatment within 28 days of confirmation.

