### **7.2.4 Cycle 1, Day 28**

- Physical exam with Weight
- Vital signs
- CBC
- CMP
- GVHD monitoring
- Adverse events
- Concomitant medications
- Disease assessment (blood)

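### The efficacy set can drop a dosed patient who dies without relapse before a qualifying assessment, and the plan does not say which assessment qualifies

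*Combined protocol and SAP*

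**What the plan says.** The synopsis (Efficacy Analyses) states: "All efficacy analyses will be provided by using Efficacy Evaluable population". Section 9.3 repeats this. In both places the set is registered patients who "received at least one dose of APR-246 or azacitidine, and have at least one efficacy assessment, or had relapse/progression". No efficacy analysis on all treated patients is described. The Safety Evaluable set (Section 9.1) needs only registration and any dose.

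Death without relapse is an event for RFS (9.3.1), OS (9.3.2), NRM (9.3.3) and EFS (9.3.5), and a competing event for TTP (9.3.4).

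The plan lists what is assessed and when, but does not tie any of it to membership of the set:

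- Synopsis, Criteria for evaluation, under efficacy: "Bone marrow aspirate and biopsy following cycle 3, cycle 6, cycle 9, and cycle 12, or when clinically indicated, and monthly CBC". The weekly first-month CBC is listed under safety.
- Section 8.2, headed as efficacy, names no visits: "CBC and differential will also be used to assess the presence of blasts in PB".
- Section 7.1.3 lists a disease assessment before the first dose, and Section 7.1.4 has treatment start after a marrow: "Once this BM biopsy confirms CR and all other eligibility is confirmed".
- Section 7.2.3 lists a CBC but no disease assessment on Cycle 1 Days 7, 14 and 21. Section 7.2.4 lists a blood disease assessment on Day 28. The Appendix B footnotes allow a window of up to 14 days for disease assessments.

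**The concern.** If an on-treatment assessment is needed, a patient who relapses early is kept and a patient who dies early without relapse is dropped. Membership of the primary analysis set then depends on an outcome that is itself a primary-endpoint event. Dropping those deaths biases RFS, EFS and OS upwards and NRM downwards, and NRM loses its earliest events. OS needs no disease assessment, so the restriction has no rationale there.

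Because the qualifying assessment is undefined, the choice could be made after outcomes are known. With 31 patients in a single arm, one or two exclusions are visible in the result.

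**Working it through.** **Inputs.** From Section 9.2: n = 31; one-sided alpha 10%; 1-year RFS 30% (null) and 50% (alternative); exponential RFS; 24 months of accrual and 12 of follow-up; 1-year relapse about 40% and NRM about 30%. The last two give a non-relapse share of events of 30/70 = 3/7. Carrying that share to the alternative is an assumption.

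**The plan's own figures.** Hazards are -ln(0.30) = 1.204 and -ln(0.50) = 0.693 per year, ratio 0.576. The event probability under the alternative is 1 - (0.5 - 0.125)/(2 × 0.693) = 0.7295, so 31 × 0.7295 = 22.6 events (stated 23). Power is Φ(√22.6 × 0.552 - 1.282) = 91.1% (stated 90.1%). The sample-size figures reproduce to within about a point; the issue is the analysis set.

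**Loss by reading.** With constant hazards from first dose, the chance of a non-relapse death before day d is p = (3/7)(1 - exp(-h·d/365.25)). Expected loss is 31p, and the chance of losing at least one patient is 1 - (1 - p)^31. Apparent RFS is S/(1 - p) and apparent NRM is (NRM - p)/(1 - p). Day 42 puts every first assessment at the end of the 14-day window.

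| First qualifying assessment | p, null | Lost of 31, null | Lost of 31, alternative | At least one lost, null | RFS, null | NRM, null |
|---|---|---|---|---|---|---|
| Pre-dose | 0 | 0 | 0 | 0 | 30.0% | 30.0% |
| Day 7 CBC | 0.98% | 0.30 | 0.18 | 26% | 30.3% | 29.3% |
| Day 28 blood | 3.78% | 1.17 | 0.69 | 70% | 31.2% | 27.3% |
| Day 42 | 5.54% | 1.72 | 1.02 | 83% | 31.8% | 25.9% |

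Under the alternative, apparent RFS moves from 50.0% to 50.3%, 51.1% or 51.7% (Days 7, 28, 42).

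**Type I error.** This was simulated with 31 patients per trial, uniform accrual, time zero at first dose, statistic (O - E)/√E and excluded deaths not replaced. It is 8.6% with no exclusion, then 9.4%, 12.0% and 13.8% for Days 7, 28 and 42. The rise is 12.0 - 8.6 = 3.4 points at Day 28 and 13.8 - 8.6 = 5.2 at Day 42.

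**Sensitivity.**

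- Halving the NRM hazard over the first 42 days gives a null loss of 0.6 (Day 28) or 0.9 (Day 42). Raising it by half gives 1.7 or 2.5.
- A post-transplant azacitidine series in Section 2.4, not described as TP53-selected, had NRM of 0% at day 100 and 8% at 1 year. With day 100 counted from transplant and the 8% spread evenly over days 100 to 365, patients first dosed at Day 100 or later give 31 × 0.08 × 28/265 = 0.26 (Day 28) or 31 × 0.08 × 42/265 = 0.39 (Day 42). Patients first dosed by Day 58 give none.
- That series had 1-year RFS of 57%, so its non-relapse share is 8/43, about 19%. With this share and the null hazard, type I error is 9.9% (Day 28) or 10.7% (Day 42), a rise of about 1 to 2 points.

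**The case against.** **The text has no post-baseline qualifier.** A disease assessment is required before dosing, so on the literal words every properly screened dosed patient qualifies and nothing is lost. This stands as a possible reading. However, the set would then equal the Safety Evaluable set and both added conditions would do no work. The synopsis, which puts monthly CBC under efficacy and weekly CBC under safety, points towards Day 28.

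**Days 28 and 42 are upper cases.** They assume that no early non-relapse death had a qualifying assessment. Marrow may be done when clinically indicated (synopsis), unscheduled visits may occur (Section 7.0), and patients stopping early have an end-of-treatment disease assessment (Section 7.3). If half of these deaths had an assessment (an assumption), type I error is about 10% to 11%. This stands.

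**A reader might infer that the test exceeds its 10% level.** The documents do not support that. RFS runs from registration (9.3.1), whereas the simulation starts at first dose. With an assumed event-free gap of 14 or 28 days between them, type I error is already 13% or 19% with no exclusion. The plan also gives no variance form: without exclusion the error is about 8.5% (E), 9.8% (the mean of O and E) or 11.1% (O). Only the increase caused by exclusion can be relied on.

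**Other stronger readings fail.** Not all deaths are shut out, since death from progression can enter through the relapse/progression clause. A loss of 3.2 to 3.7 patients, if only the Cycle 3 marrow counted (Days 84 to 98), is unlikely because the plan also lists blood assessments. No safety signal is hidden: Section 4.3 pauses the study for such a death within 30 days of study drug, and Section 9.1 tabulates adverse events for every dosed patient.

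**The shift is small.** At Day 28 it is 1.2 points of RFS, against a 95% half-width of about 1.96 × √(0.3 × 0.7/31) = 16 points. This stands, but it is a systematic shift that wording can remove.

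**Conclusion.** The point holds in a limited form. A death without relapse before a qualifying assessment is excluded from every efficacy analysis, and the qualifying assessment is undefined. The effect is nil if the pre-dose assessment counts and slight if a Day 7 CBC counts. On the Day 28 to 42 reading the expected null loss is at most about 1.2 to 1.7 of 31, which raises apparent RFS by 1.2 to 1.8 points and lowers apparent NRM by 2.7 to 4.1 points.

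These sizes rest on constant hazards from first dose, the 3/7 share, and no unscheduled or end-of-treatment assessment before death. Lower early NRM shrinks them; a front-loaded hazard enlarges them.

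Dropping early deaths can only flatter OS, but the net direction for OS is less certain. A living patient who stops early and misses the end-of-treatment assessment is also excluded while still followed for survival, and losing that survivor can lower OS. Severity is minor to should-fix.

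**What to change.** In Section 9.3 and the synopsis, run RFS, OS, EFS, NRM and TTP on all patients who received any dose, which is the existing Safety Evaluable set. Count deaths as events, with non-relapse deaths as competing events in TTP. For the relapse-based endpoints, censor living patients without a post-baseline disease assessment at their last disease assessment. Keep OS censoring as it stands in Section 9.3.2.

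If an assessment-based set is kept, make it a sensitivity analysis and state whether baseline assessments and safety-visit CBCs qualify. Do not simply add death as a further route into the present set. That would admit every dosed patient who dies while still excluding living patients without an assessment, so membership would still depend on outcome.

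The cost is wording only, with no new data or visits. Reported RFS may be slightly lower and NRM slightly higher. If the baseline reading was intended, no result changes.

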#### **9.3.1 Relapse-Free Survival**

The primary endpoint, RFS, is defined as the time from the date of registration to disease relapse after SCT, or death, whichever occurs earlier. If patients discontinued treatment due to toxicity, and withdrew consent without relapse disease (RD) or death at the time of data cut off, RFS will be censored at the date of the last assessment.

RFS will be analyzed using Kaplan-Meier methodology. Kaplan-Meier curves will be plotted. Median relapse-free survival will be estimated and their 95% confidence intervals based on Brookmeyer-Crowley methodology will be calculated.

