#### **4.8 Registration**

Prior to registration and any study-specific evaluations being performed, all patients must have given written informed consent for the study and must have completed the pre-study evaluations. Patients must meet all eligibility requirements listed in Section 5.0. Patients will be registered on the study by using the [REDACTED] Interactive Web Response System (IWRS) automated patient registration system (see the Study Operations Manual for specific instructions).

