## 5.0 SELECTION AND WITHDRAWAL OF SUBJECTS

To participate in this study, patients must meet:

- Transplant and enrollment criteria in Sections 5.1.1-5.1.2; and,
- APR-246 and azacitidine treatment criteria in Sections 5.2.1-5.2.2.

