## **5.2 Post-transplant Criteria for APR-246 and Azacitidine Treatment**

### **5.2.1 Inclusion Criteria**

1. Patient has received one allogeneic transplant for AML or MDS. At time of

treatment, patient must be in morphologic remission for AML or MDS as defined as < 5% blasts for AML and ≤ 5% blasts for MDS, and in cytogenetic remission with no morphologic characteristics of acute leukemia (e.g., Auer Rods) in the BM with no evidence of extramedullary disease such as central nervous system involvement or granulocytic sarcoma. Patients with CR with incomplete count recovery (CRp or CRI) are allowed. Incomplete platelet recovery (CRp) is defined as CR with platelet count < 100 x 10^9/L. Incomplete blood count recovery (CRI) is defined as CR with neutropenia < 1 x 10^9/L with or without complete platelet recovery. Red blood cell count (RBC) and platelet transfusion independence is not required.

2. Any standard (non-study) conditioning [MAC, RIC, or NMA] will be permitted. Acceptable source of allogeneic donor hematopoietic stem cells, as defined per institutional practice (allogeneic HCT for any donor source [matched sibling, URD, mismatched URD, related haploidentical] and any graft source [BM, PB].
3. Patient is ≥ 30 days and ≤ 100 days from hematopoietic cell infusion.
4. Patient is in complete remission after the transplant and has achieved engraftment. Engraftment is defined as ANC≥500/µL and platelets ≥ 20000/µL on 3 consecutive measurements (each occurring at least 1 day apart). The patient must not have had a platelet transfusion within 7 days prior to the first measurement.
5. Patients who have developed grades II-IV acute GVHD will be allowed to initiate maintenance therapy based on the following criteria:
  - Does not require high dose steroids as defined as dosage of > 0.5 mg/kg of prednisone (or equivalent) daily dose within 1 week of post-HSCT screening
  - No escalation of systemic immunosuppression in terms of increase of corticosteroids or addition of new agent/modality within 2 weeks of post-HSCT screening. Dose adjustments (both increase and decrease) of GVHD preventative medications such as calcineurin inhibitors or sirolimus to achieve therapeutic trough levels, is allowed. Topical skin and topical gastrointestinal steroids are allowed.
6. Females must either:
  - Be of non-childbearing potential
    - postmenopausal (defined as at least 1 year without menses) prior to screening, or

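### RFS is counted from registration, but only patients dosed later are analysed, so time with almost no countable events enters the test; its length depends on a registration date the protocol leaves unclear

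*Combined protocol and SAP*

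**What the plan says.** **Time zero.** In Section 9.3.1 and the synopsis, "RFS, is defined as the time from the date of registration to disease relapse after SCT, or death, whichever occurs earlier". OS (9.3.2) and EFS (9.3.5) also start at registration.

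**Analysis set.** Under Section 9.3 all efficacy analyses use registered patients who "received at least one dose of APR-246 or azacitidine, and have at least one efficacy assessment, or had relapse/progression".

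**Condition for dosing.** Section 5.2.1 requires morphologic and cytogenetic remission at the time of treatment, and again that "Patient is in complete remission after the transplant and has achieved engraftment". Section 7.1.3 adds: "The first dose must be administered no more than 28 days after confirmation".

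**When registration occurs.** Section 4.8 says "Patients must meet all eligibility requirements listed in Section 5.0" and also requires completed pre-study evaluations. Section 5.0 includes the "APR-246 and azacitidine treatment criteria in Sections 5.2.1-5.2.2" among those requirements. Read literally, registration therefore follows the post-transplant criteria. Some text points earlier. Section 4.8 has "Prior to registration and any study-specific evaluations being performed, all patients must have given written informed consent for the study", and Section 5.0 names the pre-transplant list "Transplant and enrollment criteria in Sections 5.1.1-5.1.2". The pre-transplant exclusions in 5.1.2 time myocardial infarct from registration, although 5.2.2 repeats that clause after transplant. Section 4.8 sends the reader to the Study Operations Manual for registration instructions.

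**Test.** Section 9.2 tests 12-month RFS of 30% against 50% with a one-sided one-sample log-rank test at 10%, with 31 patients. No landmark or delayed entry is planned.

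**The concern.** A registered patient who dies before the first dose is never dosed, so the death cannot enter the analysis. A patient found to have relapsed in that interval no longer meets the treatment criteria and, on the natural reading of the set, also drops out. Every patient who is analysed nevertheless carries the interval as event-free follow-up.

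There is no control arm. The interval adds expected events to the log-rank sum without matching observed events, and it shifts the Kaplan-Meier curve to the right. Both effects favour the regimen in the trial's only formal test. OS and EFS share the origin but carry no hypothesis test, so for them the effect is descriptive.

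Section 7.3 provides an end-of-treatment date for patients who stop before receiving any study drug, so the protocol expects some undosed patients.

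**Working it through.** **Inputs (Section 9.2).** n = 31; one-sided 10%; null 30% and alternative 50% at 12 months; exponential; accrual 24 months (taken as uniform); follow-up 12 months. Hazards per month: λ0 = −ln(0.30)/12 = 0.1003 and λ1 = −ln(0.50)/12 = 0.0578.

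**Reproducing the plan.**
- Event probability under the alternative: 1 − (0.5 − 0.125)/(24 × 0.05776) = 0.7295. Then 31 × 0.7295 = 22.6 events (plan: 23).
- Null-expected events per patient under the alternative: 0.7295 × 0.10033/0.05776 = 1.267. Drift of O − E per patient: 0.7295 − 1.2671 = −0.5376.
- The standard deviation of O − E per patient under the alternative is 1.2065. It comes from variance p + 2r(r − 1)k − drift², with p = 0.7295, r = λ0/λ1 = 1.737, and k = 0.3965, the mean over censoring times u of 1 − exp(−λ1u)(1 + λ1u).
- Power = Φ[(0.5376√31 − 1.2816√1.2671)/1.2065] = Φ(1.285) = 90.1% (plan: 90.1%).

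**Effect of a gap g.** If the null hazard applies from first dose, the true time from registration is T = g + Exp(λ0), while E = Σλ0X still counts from registration. With g = 28 days (28/30.4375 = 0.920 months) for everyone, E exceeds the expected number of observed events by 31 × 0.1003 × 0.920 = 2.86. The 12-month null RFS becomes 0.30^((12 − 0.920)/12) = 32.9%.

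**Type I error by simulation.** Z = (O − E)/√E, reject if Z ≤ −1.2816, censoring uniform on 12-36 months, 200,000 trials per setting with a dose required. The gap distributions are assumptions bounded by the protocol's windows. The right-hand column keeps undosed relapsers, taking an event to be a relapse with probability 4/7 from the plan's ~40% and ~30%.

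| Gap, registration to first dose | Dose required | Undosed relapsers admitted |
|---|---|---|
| None | 8.5% | – |
| Uniform 0-3 days | 9.0% | 8.8% |
| Uniform 0-14 days | 10.7% | – |
| Uniform 0-28 days | 13.1% | 10.2% |
| Always 28 days | 19.1% | 12.2% |
| Uniform 31-128 days | 53% | 19% |
| Uniform 31-156 days | 64% | 21% |

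The last two rows are registration before transplant. Pre-screening runs from Day −28 to −1. Dosing on Day 30-100 gives 1 + 30 = 31 to 28 + 100 = 128 days. If the 28-day window runs past Day 100, the upper end is 28 + 128 = 156.

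**Undetected relapse.** The pre-dose disease assessment may be 28 days old (7.1.3). If relapses in the gap go unseen and are recorded 28 days after dosing, with gap deaths still lost, uniform 0-28 days gives 10.5% and always 28 days gives 12.9%.

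**Other forms of the test.** The plan does not state the variance used. From no gap to always 28 days, averaged variance gives 9.8-21.2% and exact Poisson 7.5-17.0%.

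**Delayed entry.** With E = Σλ0(X − g) the error is 8.5-8.7% in all scenarios. This holds by construction, because the null was generated from first dose.

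**First-dose origin with the assessment requirement kept.** If the first efficacy assessment is the Cycle 1 Day 28 disease assessment (7.2.4), dosed patients who die without relapse before it are excluded. The error is then about 12% even when RFS starts at first dose.

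**The case against.** The strongest reply is that the registration rule closes the gap. Section 4.8 requires completed pre-study evaluations as well as eligibility, and blood count, chemistry and ECG are due within 3 days before dosing (7.1.3). Registration would then fall within about 3 days of dosing, and the effect is negligible. This is a fair reading, but not the only one: Section 7.1.4 allows 28 days to dosing after all other eligibility is confirmed.

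Second, the gap is not wholly free of events. A marrow relapse can be missed before dosing and counted later, and the last clause of the set definition can be read as admitting undosed relapsers. Either brings the uniform 0-28 day figure to about 10%. This stands for relapse. It does not help with deaths without relapse, which are lost on every reading.

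Third, these are type I errors only if the 30% benchmark belongs at first dose. If it came from a cohort selected and timed in the same way as this trial's set, there would be no inflation. Section 9.2 cites published data without stating the origin, so this cannot be settled from the documents.

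A reader might infer that the test runs at twice its nominal level. That needs every patient dosed on exactly day 28. A reader might also infer registration before transplant and an error above 50%. The documents leave that possible, but Sections 4.8 and 5.0 taken together point the other way, and the manual or the body of Figure 1, neither available here, may settle it.

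**Conclusion.** The mismatch between time zero and analysis set is in the text and should be fixed. Its size cannot be fixed from the documents. Against a nominal 10% (8.5% with no gap), the type I error is about 9% if registration waits for the last pre-dose tests, and about 13% if it occurs at confirmation with dosing uniform over 0-28 days. That second figure falls to about 10% if gap relapses are retained, and 19% is the ceiling. Pre-transplant registration, less supported, gives about 53-64% with a dose required or 19-21% with undosed relapsers admitted.

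All of this assumes the plan's exponential 30% null from first dose, the stated gap distributions and no dropout. The case for acting is that the primary endpoint's time zero should not depend on how a site reads the registration rule. Confidence in the size is moderate at best.

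**What to change.** 1. **Sections 9.3.1, 9.3.2, 9.3.5 and synopsis:** start RFS, OS and EFS at first dose (Cycle 1 Day 1). Alternatively keep registration as the origin, with delayed entry at first dose in both the Kaplan-Meier estimate and the expected-event sum.
2. **Section 9.3 and synopsis:** define the primary RFS set as all registered patients who received at least one dose of either drug, with no efficacy-assessment requirement. This matches the existing Safety Evaluable Population. Changing the origin alone is not enough, because early deaths without relapse would still be lost.
3. **Section 4.8:** state the visit at which registration occurs, relative to transplant, confirmation of eligibility and first dose.
4. **Section 9.2:** state that 30% and 50% are 12-month RFS from the chosen origin in patients in post-transplant remission. Confirm that the published benchmark supports this, and recompute sample size and power if it changes.

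**Cost.** Items 1-3 are wording changes; Section 6.1.1 already requires infusion start times to be recorded. Reported RFS becomes shorter by the gap, and early deaths are counted. Item 4 may change the sample size. A first-dose origin does not by itself validate the 30% benchmark, so item 4 is needed whichever option is taken in item 1.
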